Objectives	
Aim #1: The primary aim of the study is to test the effectiveness of repeated TENS use on movement-related pain in people with fibromyalgia with random assignment to three treatments: standard care, placebo TENS and active
 
Aim #2: A secondary aim will test if pain reduction by TENS results in a concomitant decrease in fatigue and fear of movement, and an increase in function and quality of life. Outcome measures will include physical function by directly assessing daily activity with an accelerometer, as well as performing specific functional tasks
 
Aim #3: To determine if active TENS alters pain processing in women with fibromyalgia and if improvement in clinical symptoms correlates with normalization of pain processing physiology. We will evaluate change in these physiologic parameters in responders versus non-responders as assessed clinically.
 
Aim #4: To determine if PROMIS is a useful instrument for assessing outcome for fibromyalgia by comparing to the revised version of the fibromyalgia impact questionnaire (FIQ-R).

Study Design	This is a phase II randomized, double-blind, placebo controlled multi-center clinical trial. The initial phase of the study will randomly allocate subjects to receive active TENS, placebo TENS or standard care (No TENS). After participating in the 1 month random assignment, all subjects will receive active TENS for 1 month. The subjects will make 4 visits to the clinic.

Subject Population	Females with fibromyalgia.
Inclusion Criteria	
 • Participants will be 18 to 70 years of age • Women may participate in the study • Diagnosis of Fibromyalgia by 1990 ACR criteria • History of cervical or lumbar pain with fibromyalgia (this is expected in all patients since axial pain is required for diagnosis) • Current stable treatment regimen for the last 4 weeks and projected stable treatment regimen for the next 2 months. • English speaking

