Aim #4: The primary endpoints of Aim #4 are the FIQR and SF-36 prior to randomization. PROMIS modules (also obtained prior to randomization) for depression, fatigue, pain behavior, pain interference, physical function, satisfaction with social roles, and satisfaction with discretionary social activities will be summarized and compared to validated FM instruments (FIQR and SF-36). Scores from each of the PROMIS modules will be compared to corresponding FIQR and SF-36 domains (see Table 1) by estimating Pearson correlation coefficients and testing for nonzero correlation. Multiple linear regression may also be used to investigate this relationship while controlling for potential confounding variables. Finally, FIQR, PROMIS, and SF-36 will be obtained at four different time points during this study (pre-treatment, randomized phase, and non-randomized active TENS). Summaries will include values at pre-treatment, changes from pre-treatment and percent changes. In addition to changes observed in the randomized phase, linear mixed models may also be utilized where treatment status (pre-treatment, randomized treatment, and non-randomized active TENS) is treated as a time-varying covariate to estimate the impact of changes in treatment status on these outcomes.

As an exploratory analysis, further investigation of changes in pain, responder

	status, and relationships between endpoints will be conducted for data collected during the non-randomized phase and will include those with an additional month of active TENS (originally randomized to active TENS) as well as those with a single month of active TENS (originally randomized to placebo TENS and no treatment control). Finally, exploratory examinations of the relationships between changes in pain, sensory, and quality of life measures may utilize multivariate methods (e.g. partial least squares and principal component analysis) and classification and regression trees.
Safety Measures	Physical Exam Vital Signs Clinical signs and symptoms Adverse Event analysis Increased pain with testing follow-up: Participants who experience an increase in testing will be contacted the day after testing about the status of the increase in pain (Added 12/2014) Safety analysis

Schedule of Visits and Evaluations.

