Aim #3	V3-V2	Change in PPT, CPM for those who complete one month of active TENS.	
 • Classification of participants who complete one month of active TENS as responders or non-responders using published criteria⁵⁰ • Linear regression models will assess for factors that predict responders and non-responders to treatment using data obtained prior to the intervention.
Aim #4	V2 V3 V4	Prior to randomization: FIQR and SF-36. PROMIS modules for comparison to FIQR and SF-36.	
 • Pearson correlation and testing for nonzero correlation between PROMIS modules (and corresponding domains of the FIQR and SF-36. • Multiple linear regression may also be used to investigate this relationship while controlling for potential confounding variables. • FIQR, PROMIS and SF-36 will be obtained at 3 time points and summarizes as values, changes from pre-treatment and percent changes, changes observed in the randomized phase. Time points are (1) V2: pre-treatment; (2) V3 randomized phase and (3) V4 non-randomized active TENS. • Linear models may be used where treatment status ((1) V2: pre-treatment; (2) V3: randomized phase and (3) V4: non-randomized active TENS) is treated as a time-varying covariate to estimate the impact of changes in treatment status.
Exploratory Analysis		Changes in pain Responder status Relationships between endpoints Relationships between changes in pain, sensory and quality of life measures	
 • Further investigation during non-randomized phase, two months of active TENS (initially randomized to active TENS and those with a single month of active TENS (initially randomized to placebo TENS or standard care) • Multivariate methods (e.g. partial least squares and principal component analysis and classification and regression trees.

--	--	--	--

Table 3: List of equipment, form per test and measure

Area	Form	Visit	Equipment: Clipboards, Pens, Computer/Form
	Screening Log	Pre Visit	Computer/Form
Surveys	Consent	1	Computer/Form
	Health History/Demographic	1	Computer/Form
	Diagnostic Confirmation	1	Computer/Form
	Eligibility Confirmation	1, 2	Computer/Form
	FIQR	1,2,3,4	Computer/Form
	MAF	2,3,4	Computer/Form
	TSK	2,3,4	Computer/Form
	Medication	1,2,3,4	Computer/Form
	SF-36	2,3,4	Computer/Form
	PROMIS	2,3,4	Computer/Form
	IPAQ	2	Computer/Form
	PSQLI	2	Computer/Form
	PSEQ	2	Computer/Form
	PCS	2	Computer/Form
	Blinding Question Researcher and Subject	3	Computer/Form

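### Aim #4's optional treatment-status covariate is visit under another name, so the model as written cannot separate treatment from time

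*Combined protocol and SAP*

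**What the plan says.** The Aim #4 row of the Data Analysis Plan table names three occasions for FIQR, PROMIS and SF-36: "Time points are (1) V2: pre-treatment; (2) V3 randomized phase and (3) V4 non-randomized active TENS". The next bullet ties the covariate to the same occasions, with V2 as the first level: "2) V3: randomized phase and (3) V4: non-randomized active TENS) is treated as a time-varying covariate". Its declared purpose is that it "is treated as a time-varying covariate to estimate the impact of changes in treatment status". No arm term and no arm interaction is written for this model.

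The Study Synopsis (Statistical Methods, Aim #4) has the same three levels without visit labels: "treatment status (pre-treatment, randomized treatment, and non-randomized active TENS) is treated as a time-varying covariate". There the model is called a linear mixed model; the Data Analysis Plan row says only linear models. Both places make it optional.

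The Study Design row of the synopsis fixes what participants receive. Before V3: "The initial phase of the study will randomly allocate subjects to receive active TENS, placebo TENS or standard care (No TENS". Between V3 and V4: "After participating in the 1 month random assignment, all subjects will receive active TENS for 1 month".

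**The concern.** A time-varying treatment covariate is informative only if people seen at the same visit differ in treatment. Here they do not differ in status. At V3 the three randomised arms share one level. At V4 the participants first assigned to active TENS have had two months of it and the others one month, and they too share one level.

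The fitted coefficients are therefore changes in the visit mean. Natural course, regression to the mean and placebo response all enter them. An analyst who follows the text would report these as the effect of a change in treatment status, and the V2-to-V4 change would look like a benefit of active TENS whether or not there was one.

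**Working it through.** The documents give no sample size, power or effect figure for this model, so there is no stated figure to reproduce. The check is what the coefficients estimate.

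**Inputs.**
- Three arms and their treatments before V3 and V4: Study Design row of the synopsis.
- Equal arms: Planned Sample Size row, 264 in total and 88 per group (264/3 = 88).
- Status levels V2, V3 and V4: Data Analysis Plan, Aim #4 row.
- Effect sizes below are assumptions for illustration, in arbitrary score units.

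**Notation.** t3 and t4 are the mean changes from V2 that would occur without TENS. a is the active effect after one month, a2 the active effect after two months, and p the placebo effect. The no-TENS effect is 0. With complete data and no carry-over, the expected change from V2 is:

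| Arm | V3 | V4 |
|---|---|---|
| Active | t3 + a | t4 + a2 |
| Placebo | t3 + p | t4 + a |
| No TENS | t3 | t4 + a |

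**Step 1: aliasing.** On the nine arm-by-visit means, visit alone (intercept plus two indicators) has rank 3. Adding the status columns as defined leaves the rank at 3, so status adds nothing to visit. FIQR is also collected at V1 (Table 1). If V1 were included as a second pre-treatment occasion, status would still be fully determined by visit.

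**Step 2: what the coefficients are.** Averaging over equal arms:
- V3 coefficient = t3 + (a + p + 0)/3
- V4 coefficient = t4 + (a2 + 2a)/3, which is t4 + a only if a2 = a

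That is two coefficients for five unknowns.

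**Step 3: numbers (assumed, with a2 = a).**
- Case A, real effect and no trend (a = -1, p = 0, t3 = t4 = 0): V3 = (-1 + 0 + 0)/3 = -0.333; V4 = -1.000.
- Case B, no effect and pure trend (a = p = 0, t3 = -0.333, t4 = -1.000): V3 = -0.333; V4 = -1.000.
- Case C, both (a = -1, p = -0.5, t3 = -0.3, t4 = -0.5): V3 = -0.3 + (-1.5)/3 = -0.8; V4 = -0.5 - 1 = -1.5. Neither is a treatment effect.

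Cases A and B give identical results, so a larger sample would not help.

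**Step 4: with arm and arm-by-visit terms.** The design has rank 9 of 9. Active minus no TENS in V3-V2 change is -1 - 0 = -1 in case A and -0.333 - (-0.333) = 0 in case B, so the two are now told apart. In case C it is -1.3 - (-0.3) = -1.0, and active minus placebo is -1.3 - (-0.8) = -0.5.

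**Step 5: the alternative of one covariate (none, placebo, active) plus visit.** This has rank 5 of 5 and returns the assumed values in case C. But everyone is on active TENS at V4, so t4 is separated from the active effect only by assuming that this effect is the same as at V3.

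**The case against.** The strongest reply is that the model is a side analysis. It is permitted rather than required, and the main task of Aim #4 is to correlate PROMIS with FIQR and SF-36 before randomisation. This stands, and it limits the weight of the point.

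A reader might infer that the randomised information on these questionnaires is lost. The documents do not support that. The Aim #2 row of the Data Analysis Plan compares the randomised groups on V3-V2 change in quality-of-life questionnaires with the Aim #1 model, and the synopsis offers the Aim #4 model as an addition to the randomised-phase changes. One small reservation: Table 1 labels PROMIS and SF-36 as quality of life but FIQR as disease-specific, so the inclusion of FIQR under Aim #2 is likely rather than stated.

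It can also be said that the synopsis's middle level could mean the treatment each person was randomised to, and that neither text lists every model term. That reading is possible for the synopsis, but it is not spelled out there, and the Data Analysis Plan fixes the level to V3. Two analysts could fit different models from these texts, and only one of those models would estimate a treatment effect.

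The mixing of one and two months of active TENS is recognised in the exploratory analysis, which separates the two groups. That analysis names pain, responder status and relationships between endpoints, so it covers these questionnaires only in part.

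A reader might also infer from the Data Analysis Plan's looser model name that within-person correlation will be ignored. The documents do not show this: the synopsis names a mixed model for the same analysis. The two labels should simply agree.

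**Conclusion.** The point holds for the covariate as the Data Analysis Plan defines it. The aliasing with visit follows from the definition alone and needs no assumption about effects, arm sizes or missing data. The coefficient formulas do assume equal arms, complete data and no carry-over; with unequal retention the arm weights at V3 would move away from one third. The illustrative values are assumptions and say nothing about the likely size of a misstatement in this trial.

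The consequence is that this one optional model cannot meet its stated purpose. The primary endpoint, the sample size and the Aim #2 randomised comparison are unaffected. It should be corrected because the text invites a time trend to be reported as a treatment effect, and because Aim #1 already contains the right structure.

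**What to change.** In the Aim #4 text of both the Study Synopsis and the Data Analysis Plan:

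- Name a linear mixed model with randomised arm, visit (V2, V3, V4) and arm-by-visit as fixed effects, allowing for within-subject correlation, with participants analysed as randomised. This extends the Aim #1 model by one visit.
- Take treatment effects from the between-arm contrasts of V3-V2 change.
- Report V3-to-V4 changes by original arm, labelled non-randomised and confounded with time.
- If a single covariate (none, placebo, active) plus visit is preferred, state that it assumes no carry-over and the same first-month active effect in both periods. Coding both months of active TENS as one level also assumes equal one- and two-month effects.

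The cost is a change of wording; data and software stay the same. The model has nine fixed-effect parameters instead of three (9 - 3 = 6 more), so intervals will be slightly wider.
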